8.6. Clinical Laboratory Results

Clinical laboratory tests (serum chemistry and hematology) will be performed at screening and, generally, each day receiving a PF-0790180 dose, unless otherwise specified in table 28. Schedule of Assessment, of the protocol. Baseline laboratory measurements do not need to be repeated if screening measurements were performed within 3 days prior to Cycle 1 Day 1. All laboratory data will be converted to standardized conventional units for reporting purposes.

Serum chemistry tests include determination of the following parameters: glucose, sodium, potassium, calcium, chloride, phosphate, bicarbonate, blood urea nitrogen or urea, creatinine, total protein, albumin, alkaline phosphatase, aspartate aminotransferase (AST), alanine aminotransferase (ALT), total bilirubin, indirect bilirubin, uric acid, calcium, magnesium, and lactate dehydrogenase (LDH).

Hematology tests include determination of the following parameters: Hemoglobin, hematocrit, platelets, white blood cells (WBC), neutrophils, lymphocytes, eosinophils, basophils, monocytes, WBC with automated 5-part differential, red blood cells (RBC), absolute reticulocytes, reticulocytes %, Erythrocyte Mean Corpuscular Hemoglobin (MCH), Erythrocyte Mean Corpuscular Volume (MCV), and Red Cell Distribution Width (RDW).

Summaries of baseline values and changes from baseline will be presented by dose level for each assessment time point.

Serum chemistry and hematology evaluations which cannot be graded per CTCAE criteria will be summarized as counts and percentages of participants who were normal at baseline, but who became abnormal subsequently.

For serum chemistry and hematology evaluations which can be graded per CTCAE v5.0, the following summary table will be created:

- Shift summary of baseline CTCAE grade versus the worst on-treatment CTCAE grade (The highest CTCAE grade during the on-treatment period is considered as the worst grade [Grade 0, 1, 2, 3, or 4] for the summary)
- Shift summary from ≤ Grade 2 at baseline to ≥ Grade 3 postbaseline

Clinical laboratory results will be listed by participant. In addition, listings of abnormal values will be provided for hematology, chemistry, coagulation parameters. If there is at least one abnormal assessment for any parameter, all the data for that laboratory parameter will be included into the listing.

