- k. PF-07901801 is administered intravenously through a free-flowing catheter; the duration of infusion is dependent on dose level: dose levels less than or equal to 33 mg/kg infused over 60 min and doses greater than 33 mg/kg infused over 90 minutes and will have doses equal to or less than 2500 mg in 250 mL and doses 2501 mg or more in 500 mL or neat drug if the drug volume is over 500 mL. Prophylaxis for potential infusion-related reaction in accordance with institutional guidelines is acceptable. If Cycle 1 loading doses are implemented, all dosing and lab schedules for the 48 mg/kg dose will follow the schedules for dose levels 12 mg/kg and 24 mg/kg
- l. Detailed sample collection schedule provided in Table 30
- ll Detailed sample collection schedule provided in Table 29
- m. Detailed sample collection schedule provided in Table 32
- n. Detailed sample collection schedule provided in Table 31
- o. Detailed sample collection schedule provided in Table 32
- p. Assessed every 12 ± 2 weeks; telephone contact is acceptable
- q. Newly-acquired FFPE/NBF tumor tissue (tumor block preferred; if tumor block is not available, unstained slides are acceptable). Tumor tissue to be collected anytime after signing of informed consent and prior to treatment on Cycle 1 Day 1. Archival tissue from most recent biopsy is acceptable if fresh tissue specimen is not available at screening. The baseline tissue chosen should be the most recently collected specimen before the start of the study therapy and after the most recent systemic therapy. Detailed sample collection schedule provided in Table 32
- r. Does not need to be performed if previous assessment was within 72 previous hours
- s. Participants should be observed for one hour after infusion with vital signs assessment in 30-minute intervals for signs of infusion-related reaction in Cycle 1; the observation period may be removed at the investigator's discretion in participants who tolerate the infusion well and do not experience infusion-related reaction during Cycle 1.
- t. Target date for FFPE/NBF tumor tissue collection date is Cycle 2 Day 1 but can be collected anytime within 7 days prior to and up to 14 days after Cycle 2 Day 1 (i.e. Tumor tissue should be collected within a 21-day window); other times may be acceptable after consultation with sponsor; tumor block preferred; if block is not available, unstained slides are acceptable. Detailed sample collection schedule provided in Table 32

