- u. Prior to initiation of every second cycle (Cycle 7, Cycle 9, Cycle 11, etc)
- v. Cycle 5, Cycle 7, Cycle 9 and every second cycle thereafter (Cycle 11, Cycle 13, etc)
- w. Cycle 5, Cycle 7, Cycle 9 and every second cycle thereafter (Cycle 11, Cycle 13, etc): blood collection for assessment of Peripheral Receptor Occupancy, Nanostring/RNA Sequencing, TCRVβ. Refer to Table 32 for details
- x. Cycle 5, Cycle 9, Cycle 13 and every fourth cycle thereafter (Cycle 17, Cycle 21, etc): blood collection for assessment of Adaptive and Innate Immunity only. Refer to Table 32 for details
- y. FFPE/NBF tumor biopsies may be collected at response, progression, at the time of any surgical intervention, end of treatment and at investigator's discretion; tumor block preferred; if block is not available, unstained slides are acceptable. Detailed sample collection schedule provided in Table 32
- z. Seven \pm three days after last administration of study treatment
- aa. To be performed 30 + five days after last administration of study treatment or before initiation of subsequent anti-cancer therapy, whichever occurs first

Table 28. Schedule of Assessment

ACTIVITY	Screening		Cyc	ele 1		C	ycle 2	, Cycl	e 3	Су	cle 4	Subseq	luent	End of	Safety	Long-
		D	Day in Cycle]	Day i	n Cycl	e	Day i	n Cycle	Cycles 1	Day in	Treatment	Follow-	Term
							(± 3	days)		(± 3	days)	Cyc	ele	Visitz	Up	Follow-Up
												(± 3 d	ays)		Visitaa	Period
	Day -28 to -	1	8	15	22	1	8	15	22	1	15	1	15			
	1															

bb. Participants with an unresolved AE at the Safety Follow-Up visit considered possibly related to ADA formation may be asked to return to the clinic for ADA blood sampling at approximately 3-month intervals (if feasible given the underlying disease) until the AE or its sequelae resolve or stabilize at a level acceptable to the investigator and sponsor up to a maximum of 12 months

cc. All post-dose sample collection times are relative to the start of the last infusion of PF-07901801

dd. These visits have multiple collection timepoints, see Table 32 for more details

ee. These visits have multiple collection timepoints, see Table 30 for more details

ff. These visits have multiple collection timepoints, see Table 29 for more details

^{*} Only for 48mg/kg dose level. May be completed by a local lab

Table 29. Sample Collection Schedule for Analysis of PF-07901801 Concentration

Cycle	Day	Nominal Time	Allowable Time Window
1	1	pre-infusion (within 30 min)	
	1	EOI	+ 5 min

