- Blood collection for PF-07901801 anti-drug antibodies

Cycle 1 Day 8

- Brief physical examination
- Vital signs (temperature, blood pressure, pulse rate, respiratory rate)
- Serum chemistry (unless previous assessment was performed within previous 72 hours)
- Hematology (unless previous assessment was performed within previous 72 hours)
- Administer PF-07901801 (12 mg/kg, 24 mg/kg)
- 60-minute observation period after PF-07901801 infusion; vital signs assessed in 30-minute intervals
- Adverse events

- Concomitant medications and procedures
- Blood collection for PF-07901801 concentration
- Blood collection for biomarkers/pharmacodynamics

Cycle 1 Day 15

- Brief physical examination
- Vital signs (temperature, blood pressure, pulse rate, respiratory rate)
- Serum chemistry (unless previous assessment was performed within previous 72 hours)
- Hematology (unless previous assessment was performed within previous 72 hours)
- Administer PF-07901801 (12 mg/kg, 24 mg/kg, 48 mg/kg)
- 60-minute observation period after PF-07901801 infusion; vital signs assessed in 30-minute intervals
- Adverse events
- Concomitant medications and procedures
- Blood collection for PF-07901801 concentration
- Blood collection for biomarkers/pharmacodynamics

Cycle 1 Day 22

- Brief physical examination
- Vital signs (temperature, blood pressure, pulse rate, respiratory rate)
- Serum chemistry (unless previous assessment was performed within previous 72 hours)
- Hematology (unless previous assessment was performed within previous 72 hours)
- Administer PF-07901801 (12 mg/kg, 24 mg/kg)
- 60-minute observation period after PF-07901801 infusion; vital signs assessed in 30-minute intervals
- Adverse events
- Concomitant medications and procedures
- Blood collection for PF-07901801 concentration

Cycle 2 Day 1

- Complete physical examination
- Vital signs (temperature, blood pressure, pulse rate, respiratory rate, weight)
- ECOG PS
- Serum chemistry (unless previous assessment was performed within previous 72 hours)
- Hematology (unless previous assessment was performed within previous 72 hours)
- 12-lead ECG (unless previous assessment was performed within previous 72 hours)
- Urine or serum pregnancy test (female participants of childbearing potential only) must be performed and be negative prior to treatment and counseled on appropriate contraception
- Administer PLD
- Administer PF-07901801 (12 mg/kg, 24 mg/kg, 48 mg/kg)
- Adverse events
- Concomitant medications and procedures

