- Blood collection for CA-125
- Blood collection for PF-07901801 concentration
- Blood collection for biomarkers/pharmacodynamics
- Blood collection for PF-07901801 anti-drug antibodies
- Collection of FFPE/NBF tumor tissue for biomarkers/pharmacodynamics (tumor block preferred; if tumor block is not available, unstained slides are acceptable). Target date for tumor tissue collection is Cycle 2 Day 1 but can collected anytime within seven days prior to and up to 14 days after this visit (ie, tumor tissue should be collected within a 21-day window), other times may be acceptable after consultation with sponsor.

Cycle 2 Day 8 (48 mg/kg dose level only)

• Hematology, unless previous assessment was performed within previous 72 hours, may be completed by a local lab.

Cycle 2 Day 15

- Brief physical examination
- Vital signs (temperature, blood pressure, pulse rate, and respiratory rate)
- Serum chemistry (unless previous assessment was performed within previous 72 hours)
- Hematology (unless previous assessment was performed within previous 72 hours)
- Administer PF-07901801 (12 mg/kg, 24 mg/kg, 48 mg/kg)
- Adverse events
- Concomitant medications and procedures
- Blood collection for PF-07901801 concentration
- Blood collection for biomarkers/pharmacodynamics

Cycle 2 Day 15 and Beyond (at any visit)

 FFPE/NBF Tumor biopsies may be collected at response, progression, at the time of any surgical intervention, end of treatment and at investigator's discretion for biomarkers/pharmacodynamics; tumor block preferred; if block is not available, unstained slides are acceptable

Cycle 2 Day 22 (48 mg/kg dose level only)

• Hematology, unless previous assessment was performed within previous 72 hours, may be completed by a local lab.

Cycle 3 Day 1

- Complete physical examination
- Vital signs (temperature, blood pressure, pulse rate, respiratory rate, weight)
- ECOG PS
- Serum chemistry (unless previous assessment was performed within previous 72 hours)

- Hematology (unless previous assessment was performed within previous 72 hours)
- Urine or serum pregnancy test (female participants of childbearing potential only) must be performed and be negative prior to treatment and counseled on appropriate contraception
- 12-lead ECG (unless previous assessment was performed within previous 72 hours)
- Radiologic assessment of disease status (unless performed within previous 7 days)
- Administer PLD
- Administer PF-07901801 (12 mg/kg, 24 mg/kg, 48 mg/kg)

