- Adverse events
- Concomitant medications and procedures
- Blood collection for CA-125
- Blood collection for PF-07901801 concentration
- Blood collection for biomarkers/pharmacodynamics
- Blood collection for PF-07901801 anti-drug antibodies

Cycle 3 Day 8 (48 mg/kg dose level only)

• Hematology, unless previous assessment was performed within previous 72 hours, may be completed by a local lab

Cycle 3 Day 15

- Brief physical examination
- Vital signs (temperature, blood pressure, pulse rate, and respiratory rate)
- Serum chemistry (unless previous assessment was performed within previous 72 hours)
- Hematology (unless previous assessment was performed within previous 72 hours)
- Administer PF-07901801 (12 mg/kg, 24 mg/kg, 48 mg/kg)
- Adverse events
- Concomitant medications and procedures
- Blood collection for PF-07901801 concentration
- Blood collection for biomarkers/pharmacodynamics

Cycle 3 Day 22 (48 mg/kg dose level only)

• Hematology, unless previous assessment was performed within previous 72 hours, may be completed by a local lab.

Cycle 4 Day 1

- Complete physical examination
- Vital signs (temperature, blood pressure, pulse rate, respiratory rate, weight)
- ECOG PS
- Serum chemistry (unless previous assessment was performed within previous 72 hours)
- Hematology (unless previous assessment was performed within previous 72 hours)
- 12-lead ECG (unless previous assessment was performed within previous 72 hours)

- Urine or serum pregnancy test (female participants of childbearing potential only) must be performed and be negative prior to treatment and counseled on appropriate contraception
- Administer PLD
- Administer PF-07901801 (12 mg/kg, 24 mg/kg, 48 mg/kg)
- Adverse events
- Concomitant medications and procedures
- Blood collection for CA-125
- Blood collection for PF-07901801 concentration
- Blood collection for PLD concentration
- Blood collection for biomarkers/pharmacodynamics
- Blood collection for PF-07901801 anti-drug antibodies

Cycle 4 Day 15

- Brief physical examination
- Vital signs (temperature, blood pressure, pulse rate, respiratory rate)
- Serum chemistry (unless previous assessment was performed within previous 72 hours)
- Hematology (unless previous assessment was performed within previous 72 hours)
- Administer PF-07901801 (12 mg/kg, 24 mg/kg, 48 mg/kg)
- Adverse events
- Concomitant medications and procedures
- Blood collection for PF-07901801 concentration

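### In Cycles 2 and 3 only the 48 mg/kg cohort has scheduled Day 8 and Day 22 blood counts, so the SAP's worst-grade haematology tables by dose would tend to show more cytopenia at 48 mg/kg even with no true dose effect

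*SAP*

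**What the plan says.** Cycle 1 is balanced. Protocol section 11 lists haematology on Days 8, 15 and 22 for every dose level, subject only to the 72-hour waiver: "Hematology (unless previous assessment was performed within previous 72 hours".

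Cycles 2 and 3 are not. All levels have haematology on Days 1 and 15. The Day 8 and Day 22 cells of Table 28 carry an asterisk, explained as "Only for 48mg/kg dose level. May be completed by a local lab". Section 11 repeats the restriction at each visit: "Cycle 2 Day 8 (48 mg/kg dose level only", "Cycle 2 Day 22 (48 mg/kg dose level only", "Cycle 3 Day 8 (48 mg/kg dose level only" and "Cycle 3 Day 22 (48 mg/kg dose level only". From Cycle 4 the schedules are the same again.

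Table 28 footnote k adds a condition: "If Cycle 1 loading doses are implemented, all dosing and lab schedules for the 48 mg/kg dose will follow the schedules for dose levels" 12 and 24 mg/kg.

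SAP 8.6 plans a "Shift summary of baseline CTCAE grade versus the worst on-treatment CTCAE grade", where worst means the highest grade in the on-treatment period, and a shift from Grade 2 or lower at baseline to Grade 3 or higher afterwards. The planned haematology outputs are Tables 52 to 54. SAP section 8 reports safety parameters by phase and dose cohort. SAP 5.1 takes haematology from local laboratories through the EDC, so the extra 48 mg/kg counts will be in the data. SAP 8.6 also summarises values and changes by dose level at each time point. SAP 5.3 lists Days 8 and 22 of Cycles 2 and 3 as visits without the dose restriction, although it refers to Table 28 for detail.

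**The concern.** A worst-grade table takes a maximum over each participant's counts. If one cohort is counted more often over the same period, it has more chances to record a low value. SAP 8.6 does not restrict the tables to common days, report the number of counts per participant, or note the difference. A reader comparing the dose columns cannot separate a dose effect from a testing effect.

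Cytopenia is where this matters. In the earlier monotherapy study (Protocol 3.5.2.1), thrombocytopenia (21%) and neutropenia (12%) were the most frequent treatment-related events, and the one DLT was a Grade 4 platelet decrease. Short episodes are plausible on the protocol's own terms: Table 16 has a category for Grade 4 thrombocytopenia lasting 72 hours or less. Protocol 5.2 also lets cumulative safety data, not only Cycle 1 DLTs, inform a move beyond 48 mg/kg or down to an intermediate level.

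**Working it through.** The plan gives no figure of its own on this point, so there is none to reproduce.

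**1. Scheduled counts** (Table 28, section 11). Cycle 1 Day 1 serves as baseline and the Safety Follow-Up count is left out.

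| Period | 12 and 24 mg/kg | 48 mg/kg | Ratio |
|---|---|---|---|
| Cycle 1, post-baseline | 3 | 3 | 1.00 |
| Cycles 2 and 3 | 2 × 2 = 4 | 2 × 4 = 8 | 2.00 |
| Through Cycle 3 | 3 + 4 = 7 | 3 + 8 = 11 | 1.57 |
| Through Cycle 6 (+ 3 × 2) | 13 | 17 | 1.31 |
| Through Cycle 12 (+ 9 × 2) | 25 | 29 | 1.16 |

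Adding the Safety Follow-Up count gives 8 against 12 through Cycle 3 (1.50).

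**2. Chance of at least one Grade 3 or higher count through Cycle 3.** Assume the same risk q per count in every cohort and independent counts. The documents give no value for q, so a range is shown. Formula: 1 − (1 − q)^k, with k = 7 or 11. The last column is 6 × the difference; Protocol 12.1.1 allows up to about six DLT-evaluable participants per level.

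| q | k = 7 (12, 24 mg/kg) | k = 11 (48 mg/kg) | Ratio | Expected excess in six |
|---|---|---|---|---|
| 1% | 6.8% | 10.5% | 1.54 | 0.2 |
| 3% | 19.2% | 28.5% | 1.48 | 0.6 |
| 5% | 30.2% | 43.1% | 1.43 | 0.8 |
| 10% | 52.2% | 68.6% | 1.32 | 1.0 |

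**3. A single episode in Cycles 2 and 3.** Assume random onset and a duration of L days. Detection is min(1, L/14) with fortnightly counts and min(1, L/7) with weekly counts.

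| L (days) | Fortnightly | Weekly |
|---|---|---|
| 3 | 21% | 43% |
| 5 | 36% | 71% |
| 7 | 50% | 100% |
| 10 | 71% | 100% |
| 14 | 100% | 100% |

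The ratio is 2 up to 7 days, then falls, and is 1 at 14 days or longer.

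**4. With common days only** (Cycle 1 Days 1, 8, 15, 22; Days 1 and 15 from Cycle 2), every cohort has 7 scheduled post-baseline counts through Cycle 3. With equal true risk the expected difference is 0.

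**The case against.** The strongest reply is that this is a presentation matter in small descriptive tables. No between-dose test is planned, escalation cohorts have about six participants, and the expansion plans a single dose. The by-time-point summaries already allow Day 1 and Day 15 values to be compared like for like. Protocol 9.1.4 and section 10 allow additional and unscheduled tests, so a dip between visits at the lower doses may still be found. All of this is correct and limits the size of the point. It does not repair the worst-grade and Grade 3 or higher tables, which still pool unequal numbers of scheduled counts.

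A reader might infer more than the documents support:

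- **That apparent incidence doubles.** The twofold figure applies to scheduled counts in Cycles 2 and 3, and to detection of one episode of 7 days or less in those cycles. The tables cover the whole on-treatment period, where the count ratio is at most about 1.6 and falls with longer treatment.
- **That dose escalation is compromised.** DLTs and the MTD rest on the 28-day Cycle 1, where counts are equal. The documents do not name haematology by dose as the main evidence for the Phase 2 dose.
- **That loading would favour 48 mg/kg over the lower doses.** Under footnote k, a loaded 48 mg/kg cohort follows the 12 and 24 mg/kg laboratory schedule, so that imbalance disappears. It would remain only between loaded and unloaded 48 mg/kg participants.

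Replacing the all-results tables with a common-day version would also be hard to defend, because it would push observed Grade 3 and 4 results at 48 mg/kg into second place.

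**Conclusion.** The point holds in limited form. The schedule difference is explicit, the extra results enter the analysis, and the worst-grade rule does not allow for them. The direction is clear: with equal true risk, the tables tilt towards more cytopenia at 48 mg/kg. The size is modest, about 0.2 to 1.0 expected extra participant in six through Cycle 3 for a per-count risk of 1% to 10%. That rests on equal, independent per-count risks and full attendance; long episodes would reduce it. Any true dose effect would be added to it.

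The loading provision leaves a separate gap. The asterisk assigns Day 8 and Day 22 counts in Cycles 2 and 3 to 48 mg/kg without qualification, while footnote k moves that level to the other schedule if loading is used. Footnote k can be read as overriding the asterisk, so this needs clarification rather than being a plain contradiction. If both kinds of participant arise, one 48 mg/kg column could mix two monitoring schedules and two planned Cycle 1 exposures (48 × 2 = 96 and 48 × 4 = 192 mg/kg).

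**What to change.** In SAP 8.6:

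- Keep the all-results worst-grade and shift tables (Tables 52 to 54). Add a footnote on the schedule difference and report the number of haematology draws per participant by cohort.
- Add a version restricted to scheduled days common to all cohorts: Cycle 1 Days 1, 8, 15 and 22, and Days 1 and 15 from Cycle 2. Name it as the version for comparison across doses.
- If Cycle 1 loading is used at 48 mg/kg, show loaded and unloaded participants separately.

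In Protocol Table 28, the asterisk footnote and footnote k should be reconciled on whether Day 8 and Day 22 haematology in Cycles 2 and 3 applies when loading is implemented.

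The cost is some wording and one extra set of tables, with no new data or visits. The common-day version leaves out some observed 48 mg/kg results, but these remain in the all-results tables.

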8.7. Vital Signs

Vital signs (weight, temperature, pulse, respiratory rate, systolic blood pressure, and diastolic blood pressure) will be summarized with continuous descriptive statistics at screening, on day 1 of each treatment cycle, at EOT/Early Termination, and at Safety Follow-up visit. Mean change from screening (baseline) will be calculated for each

Template No.: NVA_TP_CR694 Revision 4 Reference: SOPCR008, WPCR013 Template Effective Date:15Feb2023

Pfizer Inc. / Protocol: C4971002 (TTI-622-02) IQVIA Biotech (Confidential) Project # ZZA82397

cycle/cohort.

Vital Signs will be listed by participant and summarized by cohort and visit in the SAS.

8.8.ECOG Performance Status

ECOG Performance Status (ECOG PS) will be assessed with the scale described in the protocol Appendix A, at screening, on all study treatment day 1 of each cycle, and at Safety Follow-Up visit. ECOG PS at baseline will be summarized, including number and percentage of participants.

